## 2. Recording phase

Recording is the phase in which the electromyographic signal corresponding to the action or movement being studied is obtained

## 3. Processing phase

Processing the signal is proses that the raw signal has to be prepared so that it can be easily observed and analysed. The type of processing will depend on the type of analysis we wish to make from the trace.

Many different quantitative parameters can be evaluated from sEMG data such as number of contractions, contraction magnitude, contraction duration, presence of synergistic activations, evaluations of spasticity, or measures of voluntary vs. involuntary contractions.

Surface EMG's signal parameters related to muscle contraction include time analysis and amplitude analysis. The time analysis includes length of contraction. The length of contraction is a parameter for evaluating the period of muscle contraction from manually identified start until end times.

Papazian et al. successfully used the number of contractions, maximum amplitude, median amplitude, and duration from the manually identified start and end times the contractions to measured muscle activity in acute stroke patients. They also evaluated the correlation between the number of contractions, amplitude, and duration. The participants with an MMT of 0, individuals with more contractions had greater maximum amplitude and longer duration contractions.

The primary advantage of sEMG along with its non-invasive nature, is that the signals are relatively straightforward to record and analyse (with some basic signal processing knowledge). It also provides an estimate of the overall activity of a muscle or group of muscles in contrast to the more selective nature of intramuscular recordings.

Surface EMG, however, is only suitable for recording from superficial muscles and is not appropriate for recording deep muscle activity. Recording from small muscles without contamination from surrounding muscles can be difficult and signals can be prone to cross-talk, particularly over regions where there is substantial subcutaneous fat.

Surface EMG's signal has complex nature, and the huge number of variables upon which it depends, so it is important to critically analyse the signal knowing the effects of these variables on its properties. Several years now, an

increasing number of methodological studies have been undertaken in order to clarify the role of certain experimental factors that can modify signal characteristics, thereby biasing their interpretation. These factors can be classified according to their level of influence on the signal:

1. Technical level: environmental conditions (temperature, humidity, electromagnetic fields) and technical specifications of the equipment (electrodes, electrode-skin interface properties, amplifiers, filters, data acquisition card)
2. Experimental level: measurement procedure (skin preparation, electrode configuration, electrode localisation and orientation) and contraction conditions (ergometer utilised, contraction type, muscle length, contraction level, exercise duration)
3. Descriptive level: signal processing (digitisation, signal characteristics, chosen parameters, used parameter estimates), statistical data analysis (statistical tests)
4. Physiological level: physiological characteristics of the neuromuscular system, either structural (diameter of the active fibres, spatial organisation of fibres in the motor unit and of motor units in the muscle, filtering properties of the tissues, etc) or functional (myotypology, motor unit recruitment, fatigue, muscular coordination, etc.)

## Conceptual framework

[figure not shown]

Figure 4. Conceptual framework

### Premise

Based on the above frame of mind, several premises are compiled as follows:

Premise 1 : Upper extremity weakness is the most common impairment of stroke patients.

Premise 2 : The most significant improvements of upper extremity motor function occur in the first few week post-stroke, often reaching a relative plateau after 3 months with less significant recovery subsequently.

Premise 3 : The presence of any muscle contraction when attempting to perform a movement has positive predictive value on upper extremity prognosis after stroke.

Premise 4 : Muscle contraction is present even among stroke patients characterized as flaccid.

Premise 5 : Surface EMG is useful for the initial evaluation of muscle contraction even for the stroke patients who had an MMT score of zero.

**Hypothesis :**

Based on the framework and premises above, the hypothesis is formulated as follows:

H0 : sEMG parameters cannot predicts upper extremity motor function recovery in stroke patients

H1: sEMG parameters can predicts upper extremity motor function recovery in stroke patients (premise 1,2,3,4,5)

## **MATERIAL AND METHODS**

### **Study design and setting**

This study is an analytic quantitative observational study, to analyse the quantification of MMT score, FMA-UE score and electrical signals of the anterior deltoid, biceps, triceps, wrist flexors and wrist extensors muscles based on contractions, length of contraction and amplitude parameters in patients with acute phase stroke. This study performed at Hasan Sadikin Hospital between February 2024 – July 2024.

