### **Study participants**

Potential participants will be recruited by the main researcher

Inclusion criteria:

1. Patients who are hospitalized with upper extremity weakness due to stroke on the same side which confirmed with computed tomography (CT) scan or structural magnetic resonance imaging (MRI), in the acute phase
2. Men and women aged more than 18 years old
3. Willing to participate

Exclusion criteria:

1. Cognitive impairment (MoCA-Ina score less than 26)
2. Impaired consciousness (GCS score less than 15)
3. Unstable medical conditions at time of hospitalization
4. Patients with pacemaker

5. Having other injury or dysfunction in the impaired side of upper extremity that caused restrictions on the range of joint movement and muscle weakness, such as fractures, periarthritis, or moderate-severe pain
6. Diagnosis of other neurological disease or disorders in addition to stroke (e.g., traumatic brain injury, neuropathy or radiculopathy)
7. Get treated in isolation room
8. Hypersensitivity to gel electrodes

Drop out criteria:

1. Unable to do 2 or more follow up session
2. Withdrawn by themselves

Confounding factor:

1. Stroke location
2. Stroke size
3. Spasticity
4. Rehabilitation program
5. Compliance rehabilitation
6. Stroke risk factor

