### **Sampling Technique**

The method of sampling based on consecutive samplings, that is, all stroke patients who meet the inclusion and exclusion criteria during the duration of the study.

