## Sample Size Determination

Samples are taken from research subjects that meet the inclusion criteria.

The sample size to test the pair averages then the large determination of the sample, carried out on the basis of statistical calculations by setting the 95% confidence level of the two-way hypothesis and the power test 95%.

Sample determination for categorical numerical analytical research pairs using the formula:

$$n_1 = n_2 = \left( \frac{(Z_\alpha + Z_\beta)S}{X_1 - X_2} \right)^2$$

Where:

$Z_\alpha$  = alpha standard deviation

$Z_\beta$  = beta standard deviation

$S$  = combined standard deviation.

$X_1 - X_2$  = average minimal difference that is considered significant

Type I error is determined as 5%, hence two-ways hypothesis  $Z\alpha = 1,96$

Type 2 error determined as 5%, hence  $Z\beta = 1,64$

Based on the formula, the value is entered into the sample size formula as follows:

$$n_1 = n_2 = \left( \frac{(Z_\alpha + Z_\beta)S}{X_1 - X_2} \right)^2$$

$$n_1 = n_2 = \left( \frac{(1,96 + 1,64) * 1}{1} \right)^2$$

$$= 12,96 \approx 13$$

The minimum sample size for the pre-post test group is 13 people. The minimum number of samples required is 13 samples. The minimum sample number is added to the 10% possibility of sample exclusion so that the minimum sample size is  $13 + 1.3 = 14.3 \approx 15$  samples.

According to Gay and Diehl (1992), the sample must be as large as possible. This opinion assumes that the more samples taken, the more representative they will be and the results can be generalized. The sample size depends on the type of research:

1. The research is descriptive, so the minimum sample = 10% of the population
2. Correlational research, minimum sample is 30 units
3. Comparative causal research, the sample is 30 units per group
4. Experimental research, the minimum sample is 15 units per group

Based on the opinion of Gay and Diehl (1992), the minimum sample for this study for comparative analysis is 30 people. Based on the formula above, the minimum sample size for this research is adequate, so the minimum sample size is 30 samples.

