## Dummy Table

Table 2. Dummy Table

Variable	In Hospital				Follow Up			Difference in change at 3 months
	3 days	Discharge	P-Value	1 Months	2 Months	3 Months	P-Value	
MMT score								
FMA-UE score								
Contraction								
Length of contraction								
Amplitude								

Note: For numerical data, the p value is tested using the paired T test if the data is normally distributed and the alternative Wilcoxon test if the data is not normally distributed. Then, to compare numerical variables between pairs of more than two groups using the repeated ANOVA test if the data is normally distributed and the alternative Fredman test. The significance value is based on a p value of <0.05. The \* sign indicates a p value <0.05, meaning it is significant or statistically significant.

Table 3. Characteristic Table

Variables	p-Value
Sex	
Women	
Men	
Age	
Length of stay	
Stroke diagnosis	
Ischemic stroke	
Haemorrhagic stroke	
Stroke side	
Right hemisphere	
Left hemisphere	
Dominant Hand	
Right	
Left	
Stroke severity	
Minor stroke	
Moderate stroke	
Moderate to severe stroke	
Severe stroke	
Stroke risk factor	
Hypertension	
Diabetes Mellitus	
Heart disease	
Dyslipidemia	
Smoking	
Recurrent stroke	
Yes	
No	

Note: categorical data is presented in number, frequency, and percentage, while numerical data is presented in mean, median, standard deviation, and range.

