## Outcome Measures

The investigator assessed the outcome measures. The outcome measures are MMT score, FMA UE score, sEMG parameters (contractions, length of contraction, and amplitude). It is measured at 3 days of stroke onset, the day of discharge from hospital, 1 months, 2 months and 3 months after stroke onset.

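### The February–July 2024 window, sampling throughout the study and a last visit 3 months after onset cannot all be met; how many patients are affected is not determined

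*Combined protocol and SAP*

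**What the plan says.** All references are to the combined protocol and SAP.

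- *Study design and setting* gives one pair of dates for the whole study: "between February 2024 – July 2024".
- *Sampling Technique* describes consecutive sampling of "all stroke patients who meet the inclusion and exclusion criteria during the duration of the study". No earlier enrolment cut-off is given.
- *Outcome Measures* sets the first assessment ("It is measured at 3 days of stroke onset"), a second at discharge, and then visits at "1 months, 2 months and 3 months after stroke onset". *Research Work Procedure*, item 9, repeats this schedule.
- The *Dummy Table* has three follow-up columns and a last column headed "Difference in change at 3 months".
- *Study participants* lists as a drop-out criterion "Unable to do 2 or more follow up session".
- *Sample Size Determination* states that "The minimum sample number is added to the 10% possibility of sample exclusion". It then adopts a minimum of 30 from a cited rule of thumb. The appended subject-number entry also expects 30.

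**The concern.** Followed literally, the sampling rule keeps admitting patients until the study ends, while each patient needs three months from onset to complete the schedule. Patients admitted in the second half of the window then have no 3-month assessment inside it, and those admitted in the last two months lack the 2-month assessment too.

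The 3-month visit matters. The Dummy Table reports change at that time, and both Premise 2 and the operational definition of recovery refer to a plateau after about 3 months. The planned repeated-measures ANOVA and Friedman tests, in their standard form, use only patients with every time point. The text gives no rule for patients still in follow-up when the study closes. The drop-out criterion could therefore remove people for a calendar reason that has nothing to do with their recovery or willingness to attend.

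**Working it through.** **1. The plan's own sample size.** With Zα = 1.96, Zβ = 1.64, S = 1 and a difference of 1, n = ((1.96 + 1.64) × 1 / 1)² = 12.96, rounded up to 13. Adding 10% gives 13 + 1.3 = 14.3, rounded up to 15. Both figures reproduce. The allowance takes 13 to 15; it is not applied to the adopted minimum of 30.

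**2. Length of the window.** The documents give months, not days. Taking whole months, 1 February to 31 July 2024 is 29 + 31 + 30 + 31 + 30 + 31 = 182 days.

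**3. Last onset that fits.**
- 3-month visit: onset on 30 April gives 30 July, inside the window. Onset on 1 May gives 1 August, outside it. Onsets to 30 April cover 29 + 31 + 30 = 90 days.
- 2-month visit: onset on 31 May gives 31 July, inside. Onset on 1 June gives 1 August, outside. Onsets to 31 May cover 90 + 31 = 121 days.

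There are three follow-up sessions, so a patient with onset after 31 May loses two of them if visits stop on 31 July. That meets the drop-out criterion.

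**4. Share affected if accrual is uniform over the full window (assumption).** Let F be days from onset to the visit, L the days from onset to enrolment (0 to 3, since the first assessment is at day 3) and W = 182. The share enrolled too late for a visit is (F − L) / W.

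| Visit | F | L = 0 | L = 3 |
|---|---|---|---|
| 1 month | 30 | 30/182 = 16.5% | 27/182 = 14.8% |
| 2 months | 61 | 61/182 = 33.5% | 58/182 = 31.9% |
| 3 months | 91 | 91/182 = 50.0% | 88/182 = 48.4% |

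Counting three months as 90 to 92 days widens the last row to between 87/182 = 47.8% and 92/182 = 50.5%. At 50%, 15 of 30 would lack the 3-month visit, and 30 / 0.50 = 60 enrolments would be needed for 30 patients with it. At 33.5%, about 10 of 30 would miss both later visits.

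**5. Sensitivity to the accrual period.** If visits stop at the end of July and accrual is even over the first m months, the share without a 3-month visit is about (m − 3) / m:
- m = 3: 0%
- m = 4: 25%
- m = 5: 40%
- m = 6: 50%

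Enrolling 30 in three months needs 30 / 3 = 10 patients a month; over six months it needs 5. The documents state no accrual rate. If follow-up continues to about 31 October 2024, the share is 0% whatever the accrual.

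**6. Sensitivity to the exact dates.** With accrual over the whole window, F = 91 and L = 3, a start on 29 February gives 88/154 = 57.1%. An end on 1 July gives 88/152 = 57.9%, and both together give 88/124 = 71.0%.

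**The case against.** The strongest reply is that the text allows two harmless readings. First, six months can be three of enrolment followed by three of follow-up. The sampling sentence explains what consecutive means and need not be an accrual timetable, so enrolment could end once the expected 30 are reached. Second, the dates may describe recruitment only, with follow-up running on to October. Either way nobody is affected. The research-flow figure is not shown and some pages were removed, so a timetable may exist there.

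Much of this stands. A reader might infer that about half of the patients will lose the 3-month outcome. The documents do not support that as a flat statement, because it needs uniform accrual over all six months and visits stopping in July. Three further inferences also go too far:

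- Setting a loss of about one third against the 10% allowance mixes two derivations, since the 10% belongs to the figure of 13.
- Treating the 3-month Fugl-Meyer score as the declared primary outcome is firmer than the text, which names no primary measure or time.
- The drop-out criterion sits beside voluntary withdrawal and reaches these patients only if visits really do stop on 31 July.

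Even the unfavourable case leaves about 15 patients with the 3-month visit, above the formula's 13 although below the adopted 30.

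What does not fall away is the conflict in wording. The setting section dates the study, not its recruitment; 30 is a minimum; and the sampling rule says all eligible patients. No visible passage chooses between the readings.

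**Conclusion.** The point holds as an inconsistency. The study window, sampling throughout the study and a 3-month final visit cannot all be satisfied for onsets after about 30 April 2024. For onsets after about 31 May, the 2-month visit also falls outside.

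The size is conditional. It runs from 0%, if 30 patients are enrolled by the end of April or follow-up continues to October, to about 48–50% without the 3-month visit and 32–34% without the 2- and 3-month visits. The upper figures assume whole calendar months, uniform accrual over 182 days and no visits after July. A firm prediction that half the outcomes will be lost is not supported. The target of 30 carries no allowance for such losses if they occur. Because a stated sampling rule conflicts with a stated schedule, this is more than a missing detail and should be corrected.

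**What to change.** State the recruitment period and the follow-up period separately, and make them agree with the visit schedule. Either option works:

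1. Last eligible onset about 30 April 2024, with last visits by 31 July 2024. This keeps the stated window but needs about 10 enrolments a month to reach 30, which should be checked against expected admissions.
2. Recruitment to 31 July 2024, with follow-up to about 31 October 2024.

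In *Sampling Technique*, refer to the recruitment period instead of the duration of the study. Under *Study participants*, add that visits missed because the study closed do not count as participant drop-out, and say how any such incomplete follow-up is handled in the analysis.

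The cost is either a shorter recruitment window or three more calendar months of visits that are already planned for each patient. No new measurement or analysis method is needed. Under either option the calendar loss disappears, so 30 needs no extra allowance on this account.

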### **Study participants**

Potential participants will be recruited by the main researcher

Inclusion criteria:

1. Patients who are hospitalized with upper extremity weakness due to stroke on the same side which confirmed with computed tomography (CT) scan or structural magnetic resonance imaging (MRI), in the acute phase
2. Men and women aged more than 18 years old
3. Willing to participate

Exclusion criteria:

1. Cognitive impairment (MoCA-Ina score less than 26)
2. Impaired consciousness (GCS score less than 15)
3. Unstable medical conditions at time of hospitalization
4. Patients with pacemaker

5. Having other injury or dysfunction in the impaired side of upper extremity that caused restrictions on the range of joint movement and muscle weakness, such as fractures, periarthritis, or moderate-severe pain
6. Diagnosis of other neurological disease or disorders in addition to stroke (e.g., traumatic brain injury, neuropathy or radiculopathy)
7. Get treated in isolation room
8. Hypersensitivity to gel electrodes

Drop out criteria:

1. Unable to do 2 or more follow up session
2. Withdrawn by themselves

Confounding factor:

1. Stroke location
2. Stroke size
3. Spasticity
4. Rehabilitation program
5. Compliance rehabilitation
6. Stroke risk factor

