## **Data Analysis**

Before data analysis is carried out, the data is checked for completeness and accuracy, tabulated, coded, and entered into the computer. The next data analysis aims to describe the dependent and independent variables so that it can help further analysis in more depth. Apart from that, descriptive analysis is also used to determine the characteristics of the research subjects, who are the research samples.

Data analysis to see an overview of the proportions of each variable that will be presented descriptively can be broken down into descriptive analysis and hypothesis testing. Numerical scale data such as age and others are presented with a mean and standard deviation, a maximum value, and a minimum value. The sample characteristic data in the form of categorical data is presented in a frequency distribution table. Data is recorded in the research form that has been created, then editing, verification, coding, and data entry are carried out, and then data analysis

is carried out. Statistical analysis according to research objectives and research hypotheses Data are presented as percentages (%) for categorical variables and mean  $\pm$  standard deviation (SD) for continuous variables. Statistical analysis begins with this normality test aims to find out whether the data is normally distributed or not. The statistical test used to test the data is normally distributed or not, with Shapiro Wilks (because n is less than 50). Numerical variables between pairs of two groups is compared using the paired T test if the data is normally distributed and the alternative Wilcoxon test. Numerical variables between pairs of more than two groups is compared using the repeated ANOVA test if the data is normally distributed and the alternative Fredman test. The McNemar and Marginal Homogeneity tests are used for paired categorical data. The significance of statistical test results is determined based on a p value of  $<0.05$ .

The data obtained was recorded in a special form and then processed using the SPSS version 24.0 for Windows program.

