## Operational Definition

Table 4. Operational Definition of Research

Research Variables	Operational Definition	Measuring Instrument	Result	Measurement Scale
Sex	Sex corresponds which stated on the valid ID card	ID card Family card	Male Female	Nominal
Age	The age limit is stated in years according to the last birthday	ID card Family card	Years	Numerical
Length of stay	Clinical metric that measures the length of time elapsed between a patient's hospital admittance and discharge	Medical record	Days	Numerical
Stroke diagnosis	Acute episode of focal or global neurological dysfunction that persists for more than 24 hours	Medical record and imaging result (CT-Scan, MRI)	Stroke Ischemic Stroke Hemorrhagic	Categorical
Recovery upper motor function in stroke	Improvements of upper extremity motor function, occur in the first few week post-stroke, often reaching a relative plateau after 3 months	FMA-UE	$\leq 25$ : severe 26-45 : moderate 46-66 : mild	Categorical
Stroke side	Hemisphere (side) of blood cannot flow to in the brain	Medical record and imaging result (CT-Scan, MRI)	Right hemisphere Left hemisphere	Categorical
Dominant hand	Individual's preferential use of one hand	Medical record	Right Left	Nominal
Stroke severity	The extent of the impact caused by a stroke	NIHSS score	1-4 : Minor stroke 5-15 : Moderate stroke	Categorical

Stroke risk factor	The subject's risk factors for stroke	Medical record	15-20 : Moderate to severe stroke 21-42 : Severe stroke Hypertension Diabetes Mellitus Heart disease Dyslipidemia Smoking	Nominal
Recurrent stroke	The subject has had their brain deprived of oxygen at least twice, increasing the chances of possible damage to the brain	Medical record and imaging result (CT-Scan, MRI)	Yes No	Nominal
MMT score	Physical exam to testing muscle strength. Scoring use a five-point scale defined as normal, good, fair, poor, trace and zero	Medical record	0-5	Categorical
FMA-UE score	Stroke-specific assessment tool to assess motor functioning, balance, sensation and joint functioning. Comprises 33 items related to the movements of proximal and distal upper extremity. The maximum motor performance score is 66 points	Medical record	≤25 : severe 26-45 : moderate 46-66 : mild	Numerical

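### The drop-out rule counts missed follow-up sessions whichever they are, so it does not track who has the 3-month FMA-UE

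*Combined protocol and SAP*

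**What the plan says.** Study participants lists two drop-out criteria: "Unable to do 2 or more follow up session" and "Withdrawn by themselves". Neither refers to a particular visit.

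Outcome Measures schedules MMT, FMA-UE and sEMG at day 3 and then at "the day of discharge from hospital, 1 months, 2 months and 3 months after stroke onset". The dummy table (Table 2) groups day 3 and discharge as in-hospital assessments and months 1, 2 and 3 as follow-up. The examination form in Lampiran 1 likewise numbers three follow-up rows after two earlier examinations. So there are three follow-up sessions.

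Several places point to 3 months as the time that matters. Table 2 has a separate column, "Difference in change at 3 months". The operational definition of recovery (Table 4) uses FMA-UE and describes improvement as "often reaching a relative plateau after 3 months". Premise 2 and the literature review say the same. No section names a primary outcome or a primary time point.

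On attrition, Sample Size Determination says: "The minimum sample number is added to the 10% possibility of sample exclusion". Data Analysis defines no analysis set and no method for missing data. For comparisons across more than two visits it says: "Numerical variables between pairs of more than two groups is compared using the repeated ANOVA test if the data is normally distributed", with Friedman as the alternative.

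**The concern.** The objective is whether sEMG predicts upper-extremity recovery. For a patient to inform that question at the horizon the documents describe, two things are needed: an early sEMG recording and a 3-month FMA-UE. A count of missed sessions tests for neither. Someone who skips two intermediate visits may still supply the 3-month value, while someone who attends both may not.

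Two things are at stake. First, if staff follow the rule and stop pursuing a patient after two missed visits, a 3-month outcome that could have been collected is lost from a study of 30. Second, the drop-out count reported under the rule does not tell the reader how often the 3-month outcome is missing. If attendance is related to arm function, which is plausible but not shown in the documents, removing patients by attendance also adds avoidable selection.

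**Working it through.** **Inputs from the documents.** The rule is two or more missed follow-up sessions (Study participants). The sessions are months 1, 2 and 3 (Table 2, Lampiran 1). The planned sample is 30, with a 10% allowance (Sample Size Determination).

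**Assumed input.** The documents give no probability p of missing a visit. I use 10%, 20% and 30%.

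**The plan's own figure.** ((1.96 + 1.64) × 1 / 1)² = 12.96, rounded up to 13. Then 13 + 1.3 = 14.3, rounded up to 15. This reproduces. The 10% is added to 13; the final 30 comes from a rule of thumb with no allowance added.

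**Step 1: attendance patterns (no assumption needed).**

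| Month 1 | Month 2 | Month 3 | Rule | 3-month FMA-UE | Agree? |
|---|---|---|---|---|---|
| attended | attended | attended | keep | yes | yes |
| missed | attended | attended | keep | yes | yes |
| attended | missed | attended | keep | yes | yes |
| missed | missed | attended | drop | yes | **no** |
| attended | attended | missed | keep | no | **no** |
| attended | missed | missed | drop | no | yes |
| missed | attended | missed | drop | no | yes |
| missed | missed | missed | drop | no | yes |

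Two of the eight patterns disagree.

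**Step 2: size if misses are independent, n = 30.**

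- Dropped although month 3 is attended: 30 × p²(1−p)
- Not a drop-out but month 3 missing: 30 × p(1−p)²
- Drop-out by the rule: 3p²(1−p) + p³
- 3-month outcome truly missing: p

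| p | Dropped with month 3 | Kept without month 3 | Rule drop-out | Month 3 missing |
|---|---|---|---|---|
| 10% | 0.27 | 2.43 | 2.8% | 10% |
| 20% | 0.96 | 3.84 | 10.4% | 20% |
| 30% | 1.89 | 4.41 | 21.6% | 30% |

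Usable 3-month outcomes under the written rule are 30(1−p) less the first column: 26.7, 23.0 and 19.1. If everyone attending month 3 is kept they are 27.0, 24.0 and 21.0.

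**Step 3: size if loss is monotone (a patient who misses a visit never returns).** Nobody misses months 1 and 2 and then attends month 3, so wrongful drop-outs are zero. With a constant loss h per interval, the rule drop-out is 1 − (1−h)². Setting this to 10% gives h = 1 − √0.90 = 0.0513, and month 3 is missing in 1 − (1−h)³ = 14.6%. If all loss occurs before month 1, both figures are 10%.

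**Step 4: what a 10% rule-based drop-out would mean.** About 20% missing month 3 under independence (10.4% goes with 20%), 14.6% under constant monotone loss, and 10% if all loss is early. These are three illustrative patterns, not bounds.

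**The case against.** The strongest reply is that the documents do not say that a drop-out's data are removed. The criteria sit under recruitment, Data Analysis defines no analysis set, and the exclusion allowance is not tied to this rule. That is fair. Removal is the natural reading of an allowance for sample exclusion, but it is a reading. If it is wrong, no collected data are lost; the rule still fails to identify who lacks the 3-month value.

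Month 3 is also never declared primary. That stands too, although the change column, the definition of recovery and the premise all point the same way.

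A third reply is that the planned tests are paired comparisons and repeated-measures ANOVA or Friedman, which do not use predictor–outcome pairs. A patient with only month 3 cannot enter the three-visit comparison, which in its usual form needs complete rows: at p = 10%, 30 × 0.9³ = 21.9 patients. That patient can still contribute to the 3-month change column, so the loss is real but limited to that part of the table.

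A reader might infer that keeping patients who lack month 3 is itself a fault. It is not: they supply earlier visits and should be kept. What is wrong is that the rule does not count them as missing the outcome. A reader might also hold a missing day-3 recording against this rule, but that is a question about enrolment and baseline data, which a follow-up criterion would not be expected to settle.

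**Conclusion.** The point holds as a mismatch between the retention rule and the outcome the study needs. The mismatch in two of eight patterns follows from the text alone, given that follow-up sessions means months 1 to 3.

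Its size is modest and rests on assumptions. Wrongful drop-outs are about 0.3–1.9 of 30 for independent misses at 10–30% per visit, and zero under monotone loss. The larger effect is on reporting: 10% drop-out by the rule could stand for roughly 10–20% without a 3-month FMA-UE in the patterns examined.

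It would be tempting to conclude that the rule discards endpoint data as a matter of course, that a 10% drop-out means 20% are missing, or that the results will be biased. The documents support none of these. Removal from analysis and the status of month 3 are inferred, the 20% depends on independence, and no link between attendance and arm function is shown. The change is still worth making, because the rule can cost 3-month outcomes in a small study and serves no stated purpose.

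**What to change.** - Delete drop-out criterion 1 and treat only withdrawal of consent as drop-out.
- Attempt the month-3 visit in every other patient, including those who missed months 1 and 2.
- State that all collected data are kept.
- Include in the 3-month recovery analysis every patient with an early sEMG recording and a 3-month FMA-UE, whatever happened at months 1 and 2.
- Let patients without month 3 contribute their earlier visits. As repeated-measures ANOVA and Friedman need complete rows, this calls for a method that uses all available visits, such as a mixed model.
- Report the number missing month 3, with their day-3 FMA-UE, as the attrition figure.

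The cost is a changed criterion and a few sentences in Data Analysis, plus the effort of contacting patients who would otherwise have been let go. No new visit type or measure is needed. Reported attrition may look higher than under the present rule. The 3-month analysis would still be restricted to those who attend month 3, and the report should acknowledge that selection; the day-3 comparison helps the reader judge it but does not remove it.
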